1.3. Potential Risks and Benefits

1.3.1. Known Potential Risks of MindCotine

The virtual reality simulation could potentially trigger seizures. Those with a history of epilepsy should not use this treatment option.

There is also the possibility of side effects from the virtual reality simulation. Symptoms may include dizziness, disorientation, nausea, sweating, or headaches.

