3.2.2. Retention Procedures

None. After enrollment, participants will be contacted at the end of the 6-week intervention. Unless the participant reaches out to the team during the intervention period, there is no expected contact with the participant until the end of the 6-week period.

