6.2. Description of Procedures and Assessments

6.2.1. Efficacy Assessments

1. Patients who use tobacco are identified as part of the Tobacco Treatment Program. The Tobacco Treatment Specialist reaches out to these patients and offers tobacco cessation resources, and the pilot study will be offered as a part of this. Recruitment of 20 participants is estimated to take approximately 3 months.
2. If a patient expresses interest in the pilot study, they will go through a phone screen consent and questionnaire. Inclusion criteria includes daily or some day cigarette smoking, English or Spanish fluency, have compatible smartphone, willing to commit to the intervention and complete the surveys, and no history of epilepsy.

3. Informed Consent: If a patient is eligible for the study, and would like to proceed, they will go through an informed consent process provided via online link. The Tobacco Treatment Specialist will be available to go through the consent form with the patient. If signed, they will be enrolled in the pilot study, and a copy of the signed consent form can be provided via secure email or by mail.
4. Within two business days of the informed consent, a study research team will keep track of signed consents and keep track of participants, including demographics, any tobacco cessation resources the participant also wanted to use, date of screening, when the kit was mailed out, and when end of treatment will be.
5. Within two business days of the informed consent, the study team will mail out a VR kit to the participant. The VR kit should reach the participant in 3-5 business days.
6. Once the VR kit is received, the participant can have full access to the MindCotine app and start the intervention.
7. The participant interacts with the app for 6-weeks.
8. After the 6-week intervention, the study team reaches out to the participant to complete the end of treatment survey. If the team is unsuccessful with reaching the participant after 3 attempts, the participant will be considered “lost to follow up”. The end of treatment assessment will include questions on tobacco use, satisfaction with MindCotine, likelihood of recommending MindCotine to others, and whether VR side effects were experienced.
9. Any adverse effects learned of will be tracked.
10. MindCotine will provide user app data from the 20 participants.
11. The study team will link the app data to the survey data and remove identifiers.
12. [name] will conduct data analysis.

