6.2.2. Safety and Other Assessments

During screening, patients who have a history of epilepsy are not eligible for the pilot study. The VR environment may be triggering for these patients.

At end of treatment, VR side effects will be assessed.

We do not anticipate serious adverse events as a result of an app designed for smoking cessation. Should any become known to the team, [name] will be notified within 24 hours upon learning of that information, and the team will proceed according to her directions. All SAEs will be documented. [name] is a licensed clinical psychologist and has led multiple clinical trials.

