7.4. Adverse Event Monitoring and Collection

Untoward medical events experienced by a study subject during the study intervention period (6-weeks) will be considered an adverse event (AE), regardless of whether or not considered intervention-related. All events of disease progression or second cancer will be recorded as a serious adverse event (SAE) using the Preferred Term appropriate for the clinical finding.

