4. Are you currently using any quit smoking medications?	
 a. Chantix b. Bupropion c. NRT (patches, gum, lozenges, spray) 	Original

If still smoking –
 
5. During the past 6 weeks, have you stopped smoking cigarettes for one day or longer because you were trying to quit smoking?
	
 a. Yes, stopped smoking cigarettes for one day more in an attempt to quit b. No, did not stop smoking cigarettes for one or more 	ASPiRE (modified)
6. How would you rate the MindCotine program?	
 a) Excellent b) Good c) Fair 	CSQ-8 (adapted)
7. If a friend was in need of quitting smoking, would you recommend MindCotine to them?	
 a) No, definitely not b) No, I don't think so c) Yes, I think so d) Yes, definitely 	CSQ-8 (adapted)
8. Did you experience any of the following when using the MindCotine app?	
 1. Dizziness None Mild Moderate Severe 2. Nausea None Mild Moderate Severe 3. Disorientation None Mild Moderate Severe 4. Sweating None Mild Moderate Severe 5. Headache None Mild Moderate Severe 	Original for assessing side effects of VR

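### The visible end-of-treatment survey does not ask about seizure, and no general medical-event question is described, so a zero count would mean only that none came to notice

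*Combined protocol and SAP*

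**What the plan says.** Section 1.3.1 puts seizure first among the app's risks: "The virtual reality simulation could potentially trigger seizures". It then lists five side effects: "Symptoms may include dizziness, disorientation, nausea, sweating, or headaches". A history of epilepsy is excluded in 5.6, 6.2.1 and 6.2.2, and the synopsis excludes a history of seizures.

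The planned safety collection is a single survey. Section 3.2.2 states that, unless the participant makes contact, "there is no expected contact with the participant until the end of the 6-week period". Section 6.2.2 says "At end of treatment, VR side effects will be assessed". Sections 5.11 and 6.2.1 (step 8) describe the survey as covering tobacco use, satisfaction, likelihood of recommending the program, and VR side effects. Item 8 in 13.2.1 asks "Did you experience any of the following when using the MindCotine app" and gives five numbered rows, the last being "5. Headache None Mild Moderate Severe".

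For everything else, step 9 of 6.2.1 reads "Any adverse effects learned of will be tracked". Section 7.2.4 likewise depends on the team learning of an event.

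The definition of an adverse event is much wider than the survey. Under 7.4 an untoward medical event in the intervention period "will be considered an adverse event (AE), regardless of whether or not considered intervention-related". The same section treats disease progression and second cancers as serious, and 7.1 does the same for unplanned hospitalization. Adverse events are a secondary endpoint (10.2.2), tabulated as frequencies in the full sample of 20 (10.5, 10.5.1, 10.5.2).

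**The concern.** What the plan promises to count and what it plans to ask do not match. The five VR-sickness symptoms would be solicited from everyone who answers the survey. Seizure, and any medical event not tied to app use, would be recorded only if it reached the team some other way. The two kinds of count would then sit in one adverse-event table as if they were equally well ascertained.

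The reader of the results is the one misled. No seizures or no hospitalizations among 20 participants would read as an observation, when it would mean only that nobody reported one. The downstream safeguards share the weakness: 24-hour notification (6.2.2, 7.6, 7.8), the Principal Investigator's ongoing safety review (9.3) and termination for unacceptable risk (5.11) can act only on events that have become known.

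**Working it through.** The plan states no figure to reproduce. The check is a comparison of the text in three steps.

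**Step 1. Named risks against item 8.**

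| Risk named in 1.3.1 | Row in item 8 |
|---|---|
| Seizure | none visible |
| Dizziness | 1 |
| Nausea | 2 |
| Disorientation | 3 |
| Sweating | 4 |
| Headache | 5 |

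Five of six named risks are solicited. The one left out is the risk behind the epilepsy exclusion. The stem is closed and restricted to app use, and no row for other symptoms is visible.

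**Step 2. Any other route that asks.**

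- During the 6 weeks: no study contact is planned (3.2.2).
- At end of treatment: the content described in 5.11, 6.2.1 and 6.2.2 has VR side effects as its only safety element.
- Sections 7.4 to 7.6: these define, log and report known events, but give no procedure for asking about them.
- Charts: 9.4.1 names clinical charts and hospital records as source documents, but schedules no chart review for adverse events.
- Participants not reached after 3 attempts (6.2.1, step 8): they are asked nothing, yet remain in the analysis population of 20.

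**Step 3. How complete the visible form is.** End-of-treatment items 1 and 2 are missing. Item 3 stops at blunts, although the parallel screening item ends with a *None* option. Item 4 also has no *None*, and item 6 shows nothing below *Fair*. In items 3, 4 and 6 it is the end of the list that seems to be lost, which is where a sixth row in item 8 would sit. Against that, the five numbered rows match the five symptoms in 1.3.1 exactly. The missing seizure row is therefore likely but not certain. The missing general medical-event question is better supported, because the narrative sections describe the survey content independently of the damaged table.

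**The case against.** The strongest case on the other side is that little would change in 20 people. Epilepsy is excluded at entry, which lowers the chance of a seizure. Known serious events go to the responsible lead within 24 hours. The study is descriptive and makes no claim about a seizure rate. Even if all 20 were asked and none reported a seizure, the exact one-sided 95% upper bound would be 1 − 0.05^(1/20) = 0.139, or 13.9%, so neither version of the survey would give an informative rate. That stands. The benefit of asking is to detect an individual event, not to estimate a rate.

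Four stronger readings are tempting, and the documents do not support them.

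- A reader might infer that only mild symptoms are solicited. Each row of item 8 is graded up to Severe.
- A reader might infer that a seizure could be captured only if volunteered. Participants are cancer-center patients identified through Epic, charts are source documents (9.4.1), the Principal Investigator and the monitoring committee review safety (9.3), and participants may also use other tobacco treatment services. Any of these could bring an event to light, though none asks for it systematically.
- A reader might try to size the loss by inflating the 13.9% bound for incomplete reporting. The documents give no capture fraction, so any such figure would be invented.
- A reader might infer that the adverse-event result drives the choice to adopt the app. Section 2.1.4 ties that choice to interest, onboarding, recommendation, reduction and quitting, and adverse events are not among its criteria.

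**Conclusion.** The point holds at moderate confidence. Followed as written, the plan would under-ascertain a declared secondary endpoint as 7.4 defines it. Its size is best stated as a gap in coverage: one of six named app risks has no visible question, and the wider class of medical events, including hospitalization, has none in the described survey content. A count of zero for these would mean that none was volunteered or found incidentally. The primary feasibility endpoint is untouched.

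The conclusion rests on two assumptions: that item 8 has no seizure row lost in extraction, and that 5.11, 6.2.1 and 6.2.2 describe the survey's safety content in full. If the complete form already has a seizure row, the first half of the point falls and the second remains.

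**What to change.** 1. Check the complete form. If item 8 has no such row, add *seizure, convulsion or loss of consciousness*.
2. Add one yes/no question on hospitalization or any new or worse medical problem during the adverse-event period, with date and outcome if yes.
3. State that period once. Section 7.2.4 starts at consent and 7.4 uses the 6-week intervention period; the two should be reconciled and the question worded to match.
4. Report solicited and unsolicited events separately, and give the number of participants who were never asked beside the adverse-event counts.
5. Optionally, check the Epic record of participants lost to follow-up for the same events over the same period. The consent pages are not available here, so this depends on whether consent covers it. If it does not, item 4 is enough.

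The cost is two survey lines and an IRB modification, plus a short chart check if item 5 is adopted. The drawback is that more unrelated medical events will be logged in a cancer population; the attribution step in 7.2.2 already provides for sorting them.

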13.2.2 Recruitment Guide

The Tobacco Treatment Specialist (TTS) will contact patients as part of IRB 48420. Below is a script in navy blue for when the TTS offers different treatment options. Note: Wording may be slightly altered to allow for organic conversation or clarity.

We have a pilot study going on that involves a mobile-based virtual reality program to help quit smoking. The study is to help decide on whether we should invest in the virtual reality program to offer as part of our tobacco treatment services. The virtual reality treatment involves learning skillsets to aid with quitting smoking, and the treatment can be done remotely. We are looking to recruit 20 participants. If you're interested, would you like to go through the screening interview to see if you can participate in the study?

[figure not shown]
[figure not shown]
Or

[figure not shown]
[figure not shown]
[figure not shown]
I wanted to let you know about a new opportunity we have available. It is a mobile-based virtual reality program for quitting smoking. The program teaches skills for quitting smoking and is very visual. The treatment can be done at home from your phone. We have 20 of the kits available to test out. If you're interested, would you like to go through some screening questions to see if the program would be a good fit for you?

If yes, proceed to phone screen.

If no, continue engagement as part of IRB 48420.

13.2.3 MindCotine Brochure

SRC Pre-review Comments and Recommendations:

Reviewer will input text comments here for return to the author / study team.
